## **Respiration Rate Endpoint Justification**

The Respiration Rate is derived by the CP Analytics Engine from impedance measurements taken by the CPM device for a one (1) minute period. The CP Analytics Engine performs a quality control (QC) check for 30 seconds of consecutive impedance measurement samples. This QC-validated measurement data of 30 seconds results in a maximum computational accuracy of 2 BPM for the respiration rate. Consequently, an accuracy of 2 BPM is deemed sufficient for the CPM Device's intended use.

## **Relative Tidal Volume Endpoint Justification**

Tidal volume as measured by home-care ventilators have been shown to have a partial Spearman correlation of as low as 0.59 when compared against a reference data logger (Stagnara et. al, Respiratory Care, June 19, 2018). As this variability is deemed acceptable for ventilator products in the market that require greater accuracy for delivery of pre-set tidal volume, an accuracy of  $R^2$  value > 0.5 (R > 0.7) is deemed sufficient for its intended use.

## Pathologic Cohort Data Analysis:

#### **Power Statement:**

#### Study Population Justification:

The CPM System intended patient populations are highly overlapping. Patients with heart failure tend to have several comorbidities including Chronic Obstructive Pulmonary Disease (COPD), and Coronary Artery Disease (CAD) and the vast majority of them are on oral diuretics to control their congestion. According to Medicare Advantage reporting data for 2017, 58.1% of heart failure patients were on furosemide (one of few common types of diuretics), 46.8% of HF patients had COPD, and 35.5% of HF patients had ischemic heart disease.

Similarly, COPD patients also tend to have several comorbidities including HF. For example, 39% of COPD patients have cardiovascular disease, over 25% of COPD patients have ischemic heart disease and over 18% have HF.

In addition, the focus of our study is to determine the precision of the impedance measure provided by the CPM system. We believe that the precision of the measurement itself is not dependent on the disease state and impedance measurements are commonly used by many medical devices (including patient monitors) on a variety of patient populations.

These statistics show a significant overlap between the populations that the CPM system is indicated for and our technical analysis shows that the performance should not depend on the underlying disease state. Hence, we believe that there is no need for splitting our study population into subgroups.

## Sample Size Justification:

Based on preliminary data, the standard deviation ( $\sigma$ ) of the thoracic impedance for an individual subject did not exceed 5.1  $\Omega$  when placement was controlled. Using the paired-difference equivalence test power formula, we calculate the number of subjects n needed to demonstrate that the 2 device measurements are equivalent ( $\delta = 0$ ) within 6  $\Omega$  (B = 6). To obtain a 2-sided alternative with 90% power we set  $z\alpha = 1.96$ , and  $z\beta = 1.65$ . We can then calculate the required n = 10. This suggests that with 10 subjects we would be able to demonstrate equivalence (with 90% power) if the differences in the measurements between CPM Device and the reference device are within 6  $\Omega$ . However, we know that our estimates of the standard deviation might be inaccurate since they are based on a small sample of data and did not include the same patient population. To account for that potential error, we plan to enroll 20 subjects.

## Data Analysis Plan:

## Demographics:

A table will be constructed with counts and percentages of the number of subjects who were screen failures, the number of subjects enrolled in the study, the number of subjects withdrawn from the study before study completion, and the number who completed the study. For those subjects who withdrew before completion of the study, counts and percentages of the reasons for withdrawal will be tabulated. The continuous demographic characteristics at screening will be summarized for all subjects enrolled in the study using descriptive statistics (mean, standard deviation, median, minimum, maximum, and number of non-missing observations). The categorical baseline characteristics will be summarized for the study participants using frequency counts and percentages.

## Effectiveness and Endpoint Analyses:

Thoracic Impedance from the CPM System will be derived from the CPM analytics engine as described previously in the protocol, and the equivalent parameters will be recorded from the reference device output.

For pairs of measurements collected continuously with the CPM and reference device, scatter plots with the 45degree line of agreement superimposed will be constructed from paired observations from the two sources along with Bland-Altman plots of the data. The mean absolute error (MAE) and the root-mean-square error (RMSE) estimates of agreement will be calculated for each comparison, as well as correlation coefficients. The standard deviations of each of the agreement measures will also be computed. The R^2 value for the tidal volume measurement will also be calculated.

# Endpoints

Thoracic Impedance Precision (primary)

- Std < 6 Ohms from measurement to measurement (short term) within a subject
- Std of Z to reference  $X \le 6$  Ohms for short- and long-term measurements
- Respiration Rate Accuracy (secondary)
- RMSE < 2 bpm between reference and test device
- *Tidal Volume Accuracy (secondary)* 
  - $R^2$  value > 0.5

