## **Outcome Measures:**

Primary Outcome Measures

- 1) Accuracy of CPM System calculated RR versus reference device\*
  - Correlation coefficient between reference and test device
  - RMSE accuracy
- 2) Accuracy of CPM System calculated rTV as compared to reference device calculated TV\*
  - Correlation coefficient between reference device and test device within subjects
  - Average correlation coefficients across subjects for rTV for immediate and long timeframes between measurements
- 3) Standard deviation of the difference between reference measured impedance and CPM measured impedance across multiple measurements
- 4) Average of within-subject standard deviation (STD) of TI values from test device for short term measurements

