## Pathologic Cohort

The duration per participant will be two supervised sessions of approximately one hour each. These two study sessions will take place within one day and will be separated by at least one hour. At least one safety follow-up call will occur within one week of the in-clinic session.

It is expected that the entire study duration, from the enrollment of the first participant to the completion of the final participant's site visit, will be approximately 12 weeks total, with 6 weeks allotted per cohort.

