The exercises below will then be followed, with the time of the start of each exercise recorded in the CRF. Each exercise will last approximately 2 minutes, or the time that it takes to complete one full measurement with the CPM device in measurement mode (initiated by the CPM mobile app). Reference bioimpedance will be denoted at the beginning of each measurement in both a sitting and laying down position, following the CPM Device measurement flow. All CPM Device measurements include both a Fowler and a Supine portion.

Participants will be asked to breathe normally throughout the course of all measurements, including during the final three measurements which include the use of a device that tracks respiration rate and tidal volume. Reference devices to measure skin temperature and ECG will also be used during clinic visit two, before and after the CPM Device usage.

Subjects are to be instrumented with both the ADI device and reference impedance, mouthpiece, pneumotach, sampling line for O2 and CO2, ECG, and skin temperature.

Item	Description	Device/Mode	Duration	
1	Baseline reference TI measurement*	Bioimpedance reference	1 min	
2	Baseline measurement	CPM/Baseline Setup, App	3 min	
3	Reference TI measurement	Bioimpedance reference	1 min	
4	Application 1/Measurement 1**	CPM/Patient, App	2 min	
5	Application 1/Measurement 2	CPM/Patient, App	2 min	
6	Application 1/Measurement 3	CPM/Patient, App	2 min	
7	Reference TI measurement	Bioimpedance reference	1 min	
8	Application 2/Measurement 1	CPM/Patient, App	2 min	
9	Application 2/Measurement 2	CPM/Patient, App	2 min	
10	Application 2/Measurement 3	CPM/Patient, App	2 min	
t = 1 hour				
11	Reference skin temperature, ECG data	Reference temperature, ECG devices	1 min	

12	Reference TI measurement	Bioimpedance Reference	1 min
13	Application 3/Measurement 1; RR/TV	Reference spirometer, CPM/Patient,	2 min
	measurement	Арр	
14	Application 3/Measurement 2; RR/TV	Reference spirometer, CPM/Patient,	2 min
	measurement	Арр	
15	Application 3/Measurement 3; RR/TV	Reference spirometer, CPM/Patient,	2 min
	measurement	Арр	
16	Reference skin temperature, ECG data	Reference temperature, ECG devices	1 min

\* Measurements with the bioimpedance reference device refer to the length of time that it takes to get a stable thoracic impedance reading in both a sitting and lying down position.

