\*\*Measurements with the CPM Device refer to one entire reading of the CPM System, which takes approximately 2 to 3 minutes and includes both sitting and lying down in each measurement.

Readings will not be considered "successful" or "complete" unless all CPM device errors are resolved prior to the device streaming mode. In the case that a contact or tilt error cannot be resolved, the measurement must be repeated until the data quality is deemed sufficient. If the device begins peeling away from the skin during a measurement (as noted by a participant) and the streaming data quality looks questionable, the measurement must be repeated. The IFU can be followed for troubleshooting tips regarding issue with data quality. The device may have to be replaced, the skin moisturized, or the adhesive on the device replaced. Adhesives will be replaced between each placement of the test device. Any note regarding measurement issues and steps taken to resolve these issues must be noted in the CRF.

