# **Thoracic Impedance Endpoint Justification**

To determine the required precision for an impedance monitor to detect trends of worsening cardiopulmonary conditions, we looked into clinical standards. The ESC guidelines for the diagnosis and treatment of  $HF^1$  recommend that patients with an unexpected weight gain of >2kg in 3 days should increase their diuretic or alert their healthcare team. Using this as the guide for the change to be detected, we looked into the corresponding impedance change per kg of weight gain in patients with cardiopulmonary conditions. Gudmundsson *et al.* reported a change of 2.3 kg and 4.8 ohms (~2.1 ohms/kg) in the weeks preceding a major HF event. Note that those changes were reported using an implantable device which might be different from the thoracic impedance measured by the CPM system. Early data collected by the CPM project team show that an increase in 1kg corresponds to a 2.32 ohms decrease in the thoracic impedance. For the purpose of estimating the required precision, we will assume a 20hms/kg change.

If we define an event per the ESC guideline for weight changes, (>2kg/3days), and using the conversion factor above, we get a change of 4 ohms in 3 days. In order to estimate the precision needed for the CPM system, we assume an even slower change of 4 ohms in 5 days. In order to detect a change of 4 ohms over 5 days for a patient with a known baseline, the required precision is 6.1ohms. We will set the desired precision for the CPM system at 6ohms.

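### The two primary thoracic-impedance limits test repeatability only: they are indifferent to whether the CPM follows an impedance change

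*Combined protocol and SAP*

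**What the plan says.** The pathologic-cohort Endpoints section gives two primary TI criteria. The first is "Std < 6 Ohms from measurement to measurement (short term) within a subject". The second limits the SD of CPM against reference to 6 "Ohms for short- and long-term measurements". The Outcome Measures section confirms that both are standard deviations: "Average of within-subject standard deviation (STD) of TI values from test device for short term measurements" and "Standard deviation of the difference between reference measured impedance and CPM measured impedance across multiple measurements".

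The Thoracic Impedance Endpoint Justification derives the 6-ohm limit from the precision needed "to detect trends of worsening cardiopulmonary conditions". It takes 2 kg at 2 ohm/kg as a 4-ohm change, spreads it over 5 days, and arrives at a required precision of 6.1 ohm.

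On timing, Study Duration says: "These two study sessions will take place within one day". Study Procedures asks for normal breathing throughout. Posture is the only planned change. A reference reading takes as long as is needed for "a stable thoracic impedance reading in both a sitting and lying down position", and a CPM reading "includes both sitting and lying down in each measurement". The derivation section defines TI in the lower-tilt position only; the difference between positions is reported separately as delta-Z. Primary objective 3 names delta-Z, but the Endpoints section has no criterion for it.

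**The concern.** A noise limit chosen so that a 4-ohm change can be seen is informative only if the device shows that change. An upper limit on SD, applied while the quantity hardly moves, cannot separate a device that follows impedance from one that does not. Hypothesis (b) ties TI precision and consistency to validating the intended use, and the limit is argued from trend detection. If a pass were then cited as evidence that the CPM tracks worsening, the trial would not have tested that.

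**Working it through.** **The plan's own figure.** Sample Size Justification, pathologic cohort: n = ((1.96 + 1.65) × 5.1 / 6)² = 9.42, rounded up to 10, as stated. That calculation concerns a mean difference within 6 ohm, which is not an endpoint either.

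**How far TI can move.** At 4 ohm in 3 to 5 days, drift over 2 to 3 hours runs from 4/(5 × 24) × 2 = 0.07 ohm to 4/(3 × 24) × 3 = 0.17 ohm. Only a minimum gap between sessions is given. If the readings spanned 8 hours (assumed), the faster rate gives 0.44 ohm.

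**Criterion 1** uses CPM readings alone. A frozen CPM scores its own noise, or 0 if it has none.

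**Criterion 2, SD within patients.** The procedures table has nine CPM readings after baseline, six before the gap and three after, in three applications. Pair each with the reference taken before its application. Let s_c and s_r be the CPM and reference noise SDs (assumed, 0 to 5.1 ohm), D the true change between sessions, and g the share of D that the CPM shows. The expected within-patient variance of the difference is

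s_c² + 0.75 s_r² + 0.25 (1 − g)² D².

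The factor 0.25 is 6 × 3/(9 × 8). The factor 0.75 is 3 × 2/8, from three reference values each used three times.

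| s_r | s_c | D | Frozen (g = 0) | Responsive (g = 1) |
|---|---|---|---|---|
| 0 | 0 | 0.17 | 0.09 | 0 |
| 2 | 2 | 0.17 | 2.6 | 2.6 |
| 2 | 0 | 4 | 2.6 | 1.7 |
| 5.1 | 0 | 4 | 4.8 | 4.4 |

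All are below 6 ohm. In simulated trials of 20 patients the frozen CPM passed both criteria in 99 to 100% of runs in every row. Without noise, 0.5 × D exceeds 6 only when D exceeds 12 ohm, three times the target change.

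**Criterion 2, SD pooled over patients.** The SD now also contains patient-to-patient offset between devices and noise in the frozen baseline value. Simulated pass rates for a frozen CPM, with reference SD 2 to 2.83 ohm (all inputs assumed):

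- No offset, noise-free baseline: 100%.
- Baseline noise SD 5.1, no offset: 81% down to 66%.
- Offset SD 6, noise-free baseline: 45% down to about 30%.
- Both: 6% down to 3%.

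**Can the collected data test response?** Each patient has nine CPM readings and four reference readings (items 1, 3, 7 and 12), each in both positions. Assume independent noise per position, with CPM SD 5.1 and reference SD 2. The standard error of a patient's mean CPM posture change is 5.1 × √2/√9 = 2.40 ohm. The error variance of the reference mean is 2 × 2²/4 = 2. For a fully responsive CPM and 20 patients:

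| Between-patient SD of posture change | Slope CI above zero | Mean CI excludes zero (mean change 3 ohm) |
|---|---|---|
| 1 | about 16% | over 99% |
| 1.5 | about 41% | over 99% |
| 2 | about 70% | 98% |
| 3 | 96% | 91% |

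Reference noise also flattens the slope: at SD 2 its expected value is 4/(4 + 2) = 0.67 for a perfectly responsive device.

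**The case against.** The strongest reply is that TI is framed as precision and consistency throughout: in hypothesis (b), objective 3, Study Design and the endpoint heading itself. The intended use is to measure, record and transmit, and nowhere does the plan say a pass will be reported as validated trend detection. This stands, and it is why the first remedy is a sentence limiting the claim. It does not remove the gap, because the 6-ohm value is defended only by detection of a change.

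Second, response is not merely assumed. The justification cites early CPM data of 2.32 ohm/kg and plans on the lower 2 ohm/kg; 2 kg × 2.32 = 4.64 ohm. A reader might infer that the CPM shows only a fraction of a true change. Nothing in the documents supports that. The point is only that this trial does not confirm the early figure.

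Third, correlation, RMSE and Bland-Altman plots are planned for TI. No TI limit is attached to them, and a correlation driven by differences between patients says little about change within one.

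Fourth, a reader might infer that the limits favour a non-responding device. They do not. With equal noise (SD 2 on both devices) and drift of 0.17 ohm, criterion 1 is 1.9 ohm for both a frozen and a responsive CPM and criterion 2 is 2.6 ohm for both. Any advantage for the frozen device comes from assuming it quieter, and the 5.1 ohm in the plan is a ceiling on an individual's SD.

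Finally, posture response is delta-Z, not multi-day change in lower-tilt TI. That stands and limits what the remedy can show.

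**Conclusion.** The concern holds in a limited form. The two limits support a statement about repeatability and are silent on response. With within-patient SDs, a frozen CPM passes both in 99 to 100% of simulated trials, even with the full 4-ohm change between sessions and reference noise up to 5.1 ohm. The statement that a frozen CPM passes cannot be extended to every reading of criterion 2. If the SD is pooled, large offset or baseline noise can make it fail (3 to 81% passing in the noisy settings above), and the Endpoints section does not say which SD is meant. References in the justifications to an individual subject and a known baseline favour the within-patient reading. The noise SDs, offset SD and size of the posture change are assumptions; the drift and the 12-ohm threshold follow from the plan's own rate and schedule.

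**What to change.** In the pathologic-cohort Endpoints section:

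1. State that meeting the two SD limits supports a claim of TI repeatability only, and say whether the second SD is within patients or pooled.
2. Under primary objective 3, add a delta-Z comparison from the sitting and lying readings already taken with both devices. For each patient, set the mean CPM posture change against the mean reference posture change. Report the mean of each, their difference and the slope, with 95% CIs based on patients.
3. Allow wording about response to impedance change only if the CPM mean posture change is in the reference's direction with a CI excluding zero, or the slope's CI lies above zero. Otherwise keep the claim to repeatability.
4. State that posture response is supportive evidence and does not prove response to fluid change over several days.

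Do not gate on the slope alone: a fully responsive device would miss that condition in about 30 to 84% of trials at between-patient SDs of 2 down to 1 ohm. Do not require a slope of 1, since the electrode positions differ and reference noise flattens it. With two routes, a CPM with no posture response could earn the wording by chance in at most about 2 × 2.5% = 5% of trials.

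The cost is plan wording, one more analysis and possibly a narrower claim. No new readings are needed. The change should be fixed before the data are examined.

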## **Objectives:**

Primary Objectives

1) Validate Respiration Rate (RR) accuracy derived by the Cardiopulmonary Management (CPM) System in the range of 6-40 BPM\*

- 2) Validate relative changes in tidal volume (rTV) derived by the CPM System\*
- 3) Validate consistency in measurement-to-measurement and day-to-day changes in median Thoracic Impedance (TI) as well as position-dependent Delta Impedance ( $\Delta Z$ ) derived by the CPM System

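### The long-term impedance criterion is a standard deviation only, so a 4-ohm shift in CPM minus reference shared by all patients between the two sessions would generally pass

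*Combined protocol and SAP*

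**What the plan says.** The third primary objective concerns the consistency of thoracic impedance from measurement to measurement and from day to day. Under Endpoints in the pathologic cohort analysis there are two primary impedance criteria. The first is "Std < 6 Ohms from measurement to measurement (short term) within a subject". The second requires the SD of CPM impedance against the reference to be no more than 6 "Ohms for short- and long-term measurements". Outcome Measures defines that second statistic as "Standard deviation of the difference between reference measured impedance and CPM measured impedance across multiple measurements".

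The Thoracic Impedance Endpoint Justification derives the limit from a weight-gain event: "we get a change of 4 ohms in 3 days". It then says: "In order to detect a change of 4 ohms over 5 days for a patient with a known baseline, the required precision is 6.1ohms". The limit is set at 6.

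The pathologic Sample Size Justification uses a preliminary SD "of the thoracic impedance for an individual subject did not exceed 5.1" ohms. It describes the aim as showing equivalence "if the differences in the measurements between CPM Device and the reference device are within 6" ohms. Effectiveness and Endpoint Analyses adds scatter and Bland-Altman plots, MAE, RMSE and correlations, with no limit on any of them for impedance and no comparison of sessions.

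In the pathologic procedures table, session 1 has Applications 1 and 2 (items 4-6 and 8-10) and session 2 has Application 3 (items 13-15). A reference reading precedes each application (items 3, 7 and 12). The sessions fall on one day, at least one hour apart.

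**The concern.** The device is meant for trending. A constant offset between CPM and reference does no harm there and is reasonably left out of a precision endpoint. A change in that offset over time is different: it is the inconsistency that the third objective asks about, and averaging more readings does not remove it. A real physiological change seen by both devices cancels in the difference, so what remains is measurement shift.

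An SD is centred on its own mean. It measures scatter well and a shared movement poorly. Nothing in Endpoints or in Effectiveness and Endpoint Analyses estimates or limits the change in mean CPM minus reference from session 1 to session 2. The cohort was sized for equivalence of the two devices' measurements, but no test of a mean difference follows. A systematic shift as large as the change the device should detect could therefore sit inside a successful result without being reported.

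**Working it through.** **Plan's own figure.** n = ((1.96 + 1.65) × 5.1 / 6)² = 9.42, rounded up to 10. The stated 10 reproduces. The calculation takes a true difference of zero and a 6-ohm margin.

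**Inputs.** Limit 6 ohms; scatter s = 5.1 ohms; change of interest 4 ohms; six session-1 and three session-2 CPM readings; 20 patients. One assumption matters: 5.1 is given as the SD of thoracic impedance in an individual, and is used here for the SD of CPM minus reference.

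**Largest common shift D that still meets the limit.** The plan does not say which readings enter the SD, so four versions are shown. Each solves s² + added variance = 36. At s = 5.1 the room left is 36 − 26.01 = 9.99.

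| Readings in the SD | Added variance | Largest D at s = 5.1 | SD when D = 4 |
|---|---|---|---|
| Nine readings within patient | D²/4 | √39.96 = 6.32 | √30.01 = 5.48 |
| Three application means | D²/3 | √29.97 = 5.47 | √31.34 = 5.60 |
| Two session means | D²/2 | √19.98 = 4.47 | √34.01 = 5.83 |
| All differences pooled, 5.1 as pooled SD | 2D²/9 | √44.96 = 6.70 | √29.57 = 5.44 |

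Every version admits a 4-ohm shift. At s = 3 the largest D runs from 7.35 to 11.02. In the other direction, 4 ohms would reach the limit once s exceeded √(36 − 8) = 5.29 (session means) to √(36 − 3.56) = 5.70 (pooled).

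**Chance of passing, 20 patients, nine-reading within-patient SD (simulation).** With independent errors at s = 5.1, a 4-ohm shift passes 96% to 99% of the time and a 6-ohm shift 62% to 79%. The range reflects whether patient SDs are combined as a root mean square or averaged. With separate within-application and placement SDs of 2, 3 or 3.6 each, and a reference SD of 1, a 4-ohm shift passes 97% to 100% of the time and a 6-ohm shift about 76% to 100%. The 3.6 setting corresponds to the plan's figure, since √(2 × 3.6²) = 5.09.

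**Between-patient offsets in a pooled SD.** Take an assumed offset SD of 4 ohms. With no shift at all, the expected pooled SD is √(2c² + 1 + 16), which is 5.00, 5.92 and 6.55 for c = 2, 3 and 3.6. The offsets alone use up most or all of the allowance. In that setting a 6-ohm shift passes 75%, 20% and 3% of the time.

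**Precision of a direct estimate of the shift.** Session 2 has one application and session 1 has two, so the per-patient variance is 1.5 × (c² + c²/3 + 1). For c = 2, 3 and 3.6 the SD is 3.08, 4.42 and 5.24. The 95% half-width, 2.093 × SD/√20, is 1.44, 2.07 and 2.45; the simulated average is about 1.4 to 2.4. If the whole 5.1 were shared within an application, the SD would be 5.1 × √1.5 = 6.25 and the half-width 2.9.

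**The case against.** Several counter-arguments have weight.

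- **Any shift passes.** A reader might infer that a shift of any size passes. That needs an SD computed inside each session or on change scores. An SD taken inside session 2 alone is really a short-term SD, so the more natural long-term SD spans both sessions and does rise with a shift. The plan leaves the choice open, so the documents do not establish total blindness.
- **A 6-ohm shift would be called consistent.** This cannot be stated as a general fact. At 5.1 ohms it fails under the application-mean and session-mean versions, it often fails even under the nine-reading version, and it mostly fails if sizeable between-patient offsets are pooled. In the pooled case, though, offsets that are harmless for trending drive the failure, and a device with no shift could fail too.
- **The device drifts.** Nothing in the documents shows this. The sessions are hours apart on one day, whereas the 4-ohm change is judged over 3 to 5 days of brief daily wear. A warm-up effect repeated at each use would be a constant offset.
- **The descriptive statistics respond to bias.** MAE, RMSE and Bland-Altman plots do, but without a split by session they do not isolate a change between sessions.
- **A session comparison is confounded.** The mouthpiece is used only in session 2, after the item 12 reference reading. The reference electrodes stay on all day while the CPM adhesives are renewed. This stands, and it weighs against imposing a hard limit.

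**Conclusion.** The point holds in a limited form. The only long-term impedance criterion is an SD, and the plan neither estimates nor limits a shared session-to-session shift in CPM minus reference. At the plan's 5.1 ohms the tolerated shift is about 4.5 to 6.7 ohms across four ways of forming the SD, so 4 ohms would generally pass.

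This rests on using 5.1 for the SD of the difference, and on that scatter staying below about 5.3 to 5.7 ohms. Pooling between-patient offsets could turn a pass into a failure, but it would not make the criterion a test of drift. The finding concerns what this validation could detect within one day. It is not evidence of drift, and it says nothing about shifts over several days. It should be corrected before analysis, since the remedy needs no new data.

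**What to change.** Amend Effectiveness and Endpoint Analyses and Endpoints for the pathologic cohort:

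1. Define the long-term SD as the within-patient SD of CPM minus reference across both sessions, pairing each reading with the reference taken before that application (items 3, 7 and 12). State how patient SDs are combined.
2. For each patient, compute mean CPM minus reference in session 2 (items 13-15 minus item 12) less that in session 1 (items 4-6 minus item 3, and items 8-10 minus item 7). Report the mean over patients with a t-based 95% confidence interval beside the SD result.
3. Read the interval against the plan's own 4-ohm change. If it does not exclude a shift of that size in either direction, do not claim long-term consistency on the SD alone.

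Whether to make this a formal pass/fail rule is the sponsor's choice. A rule on the point estimate alone would pass a true 4-ohm shift about half the time.

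The cost is a few lines of analysis and possibly a less favourable conclusion. In simulation with component SDs of 2 to 3.6, a device with no shift has its interval inside ±4 ohms in 80% to 100% of runs. If the full 5.1 ohms were shared within an application, that falls to about 55%. The report should state that the shift also contains any mouthpiece effect and any ageing of the reference electrodes, and that it covers within-day drift only.
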